End of data collection (SLR)	25 June 2018
Final report of study results (SLR)	9 July 2018
Meta-analysis protocol	16 November 2018 (version 1.2)
Registration in the EU PAS register	TBC
Statistical analysis plan	10 September 2018
Meta-analysis report	November 2018

7. Rationale and background

Cleft lip and palate are the most common congenital anomalies of the craniofacial regions occurring at a rate of 1 in 700 births (1-3). Unilateral cleft lip and palate is the most common diagnosis followed by isolated cleft lip. It is more common in males. (4). The most common manifestation of these anomalies is difficulty in feeding. Individuals also experience speech, hearing and dental problems (5).

The development of cleft lip and palate is well documented. Between 4-8 weeks of gestation, normal lip development occurs along with frontonasal prominence. Nasal placodes develop and divide the paired medial and lateral nasal processes (5, 6). By the end of week 6 of gestation, the primary palate is formed by the fusion of paired medial processes and developing premaxilla (central upper lip, maxillary alveolar arch and four incisor teeth, and hard palate). During week 6-12, the secondary palate develops along with medial projections of maxillary processes. Cleft of lip and/or palate is a result of the disruption of normal development which could be due to chemical and environmental factors(7, 8)

Corticosteroids have a wide range of clinical uses. However, its use in pregnancy is limited (9).

Corticosteroids fluctuate in their ability to cross the placenta (10). Fetal concentrations (although lower than maternal concentrations) are linearly related to maternal (cortisol) concentrations (11). Pregnancy enhances systemic absorption of inhaled corticosteroids as it increases maternal tissue perfusion. This leads to the assumption that exposure of corticosteroid in pregnancy might cause congenital anomalies (11-13).

Some epidemiological studies have reported 3-6 fold increased risk of orofacial cleft due to corticosteroid use in early pregnancy or in first trimester in humans (14-16), while, some studies have not found this association (16, 17). Thus, there remains a controversy on the implication of glucocorticoid use in pregnancy. Therefore, it is important to gather more evidence related to the risk of cleft palate in neonates following exposure to glucocorticoids during pregnancy.

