9.1 Study design

Meta-analysis will be conducted with 18 observational studies previously identified through a systematic literature review which was conducted using keyword and MeSH terms on Embase and Medline via Ovid® (see Appendix 1).Articles published up to 25 June 2018 have been reviewed. Additionally, a supplementary search was conducted on the Cochrane database and general sources such as Google Scholar to identify additional studies that might be relevant to the scope of the search.

All records retrieved from the literature searches were screened for relevancy based on eligibility criteria (inclusion/exclusion). The results were initially screened by title and abstract, and the shortlisted results were further screened on full text. Relevant back references from the shortlisted studies have also been reviewed. The key outcomes reported were OR followed by RR for developing orofacial cleft(s) in neonates due to exposure of women to glucocorticoids in pregnant women

Meta-analysis is a powerful tool to analyse rare outcomes as individual studies provide inadequate power to test rare outcome. Meta-analysis increase precision in estimating effects.

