9.2 Setting

Pregnant women exposed to any glucocorticoid or corticosteroid or steroids in early pregnancy or first trimester of pregnancy irrespective of mode of administration identified through a systematic review of articles published up to 25 June 2018 by pre-specified inclusion and exclusion criteria (see section 4 of SLR in see Appendix 1). In total 18 observational studies have been selected for this meta-analysis with sample size for individual studies ranging from 106 to 832,636 patients.

- Source: Embase and Medline via Ovid®, Cochrane database, Google Scholar
- *Population sampling strategy:* All records retrieved from the literature searches were screened for relevancy based on eligibility criteria (inclusion/exclusion). The results were initially screened by title and abstract, and the shortlisted results were further screened on full text. Relevant back references from the shortlisted studies have also been reviewed.

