9.3 Variables

9.3.1 Exposure definition

The primary exposure of interest is glucocorticoid use.

• First trimester exposure: At least one prescription for glucocorticosteroids redeemed from the first day of the last menstrual period to the end of gestational week 12

OR

• Early pregnancy: At least one prescription for glucocorticosteroids redeemed from 30 days before estimated conception to the end of the first trimester

Our primary comparison group includes women not using glucocorticoid during pregnancy.

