9.7 Data analysis

- Direct treatment comparison: Any glucocorticoid or corticosteroid or steroids use irrespective of mode of administration vs. no use of glucocorticosteroids
- Model: Fixed effect model will be used. We assume that the underlying effect size is the same across the studies. The differences in observed effects are only due to random error or sampling error within the studies. The observed effects mainly depend on the sample size and weighted average mean might give a precise estimation of the overall effect. However, any deviation from this assumption will be discussed.
- Measure of relative effect: For the dichotomous outcomes will be assessed by Odds ratio (OR). Given that the event of our interest is a rare outcome, we assume relative risk (RR) equivalent to OR.
- Inverse variance method: Studies with less variance or standard deviation are given more weight. The variance of weighted average can be minimized through this method and hence inverse variance method will be used to assess the direct treatment effect
- Effect size is assessed by Odds ratio (OR) as it is a rare outcome
- Publication bias: Reporting or publication bias will be assessed by using the funnel plot (symmetry or asymmetry) and it again confirmed by using the Egger's test (in case of asymmetry funnel plot). Further, any outliers in the effect size will be determined by Galbraith plot
- Sensitivity analysis: In order to know the robustness of the findings, sensitivity analysis will be performed with and without outlier studies so that any uncertainty can be determined. This will be done only in case of high level of heterogeneity observed. However, plausible reasons for high heterogeneity (unexplained variation) will be discussed in the MAR
- Sub-group analyses will be performed for
 - Route of administration:
 - Topical
 - Systemic
 - Any other form of use
 - Types of orofacial cleft
 - Cleft lip (CP)
 - Cleft lip with or without palate (CLP)
 - Cleft palate (CP)
 - Orofacial cleft (OC)
 - Potency of glucocorticoid
 - Mild
 - Moderate
 - Potent
 - Very potent
- 95% credibility intervals will be used as a measure for the expression of the difference (overlap / no overlap with 1 for OR)
- Data will be analysed by using the metafor package in R software version 3.5.1

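### Inverse variance is the only pooling estimator stated for a rare outcome; where exposed cases are few and the comparison group is much larger, it shifts the pooled OR upward under no effect

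*Protocol*

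**What the plan says.** Section 9.7 sets out a fixed-effect analysis: "Fixed effect model will be used. We assume that the underlying effect size is the same across the studies". The reason given for the weighting is that it minimises the variance of the weighted average, and "hence inverse variance method will be used to assess the direct treatment effect". The abstract (section 4) repeats the choice. Neither place names a second estimator. The only sensitivity analysis removes outlying studies, and only if heterogeneity is high. Results are read by whether the 95% interval overlaps an OR of 1. Subgroup pools are planned by route, cleft type and four potency levels.

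The data are sparse by the protocol's own account. Section 7 puts clefts as "occurring at a rate of 1 in 700 births". Section 9.1 says: "Meta-analysis is a powerful tool to analyse rare outcomes as individual studies provide inadequate power to test rare outcome". Section 9.2 reports 18 studies, "with sample size for individual studies ranging from 106 to 832,636 patients". Section 9.3.1 sets the comparator: "Our primary comparison group includes women not using glucocorticoid during pregnancy". Section 9.9 shows that case-control studies are in the pool. Exposed cases per study, exposure prevalence and the mix of designs are not given.

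**The concern.** The stated reason for inverse variance holds when a study's weight is independent of its estimate. In sparse tables it is not. With few exposed cases and a large comparison group, the variance of the log OR is roughly 1/(exposed cases). A study that by chance has more exposed cases gets a higher OR and a larger weight; one with fewer gets a lower OR and a smaller weight. The pooled value moves up even when exposure does nothing.

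Because results are read against 1, a shift of this kind can change the reading of a safety question. The planned outlier analysis would not show it, since no single study need be outlying. The strata are where it bites: the request behind the study concerns cleft palate and the sponsor's product is topical, and both are subgroups with fewer exposed cases than the primary pool.

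**Working it through.** The protocol states no event count, expected OR or precision, so there is no figure to reproduce. The check is a hand example followed by simulation.

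**Inputs from the protocol:** risk 1/700 (section 7); 18 studies of 106 to 832,636 (section 9.2); fixed-effect inverse variance, intervals read against 1 (section 9.7). **Assumed, because not given:** exposed cases per study, exposure prevalence, group ratios and the handling of zero cells.

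**Formulas.** For a table with exposed cases a, exposed non-cases b, unexposed cases c and unexposed non-cases d: y = ln(ad/bc), v = 1/a + 1/b + 1/c + 1/d, weight w = 1/v, pooled OR = exp(Σwy/Σw).

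**Hand example.** Two cohorts, each with 3,500 exposed and 70,000 unexposed. Expected cases are 3,500/700 = 5 and 70,000/700 = 100. Let chance give 3 exposed cases in one and 7 in the other, an average of exactly 5, with 100 unexposed cases in each. The 1/b and 1/d terms are negligible.
- 3 cases: OR about 0.6, y = -0.511, v = 1/3 + 1/100 = 0.343, w = 2.91.
- 7 cases: OR about 1.4, y = 0.336, v = 1/7 + 1/100 = 0.153, w = 6.54.
- Pooled y = (2.91 × -0.511 + 6.54 × 0.336)/9.45 = 0.075, so the OR is about 1.08, although the 10 exposed cases equal the 10 expected.

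**Simulation, true OR 1, 18 equal cohorts, 20 unexposed per exposed, 0.5 added to tables with a zero cell:**

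| Expected exposed cases per study | Median pooled OR | Intervals wholly above 1 (nominal 2.5%) |
|---|---|---|
| 1 | 1.41 | 32% |
| 5 | 1.10 | 13% |
| 10 | 1.05 | 9% |

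Mantel-Haenszel on the same tables has a median of 0.99 to 1.00. At 5 cases per study only 0.6 to 0.7% of tables contain a zero cell, so a zero-cell rule alone would not remove the shift. At 20 and 50 cases per study the mean pooled OR is 1.02 and 1.01.

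**Interval width.** The mean model standard error against the empirical standard deviation of the pooled log OR is 0.228 against 0.198 at 1 case and 0.109 against 0.103 at 5. The intervals are slightly wide, not narrow; the excess above 1 comes from the shifted point estimate.

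**Direction.** Equal exposed and unexposed groups give 1.00 at every case count. Case-control pools of 18 studies give:
- 500 cases, 500 controls, 2.5 expected exposed cases: 1.00.
- 500 cases, 2,500 controls, 2.5 expected exposed cases: 1.16.
- 1,000 cases, 500 controls, 5 expected exposed cases: 0.91, with 4.1% of intervals wholly below 1.

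In the last case the variance is driven mainly by the exposed controls, so the weight rises as the OR falls. In case-control studies sparseness depends on exposure prevalence and case numbers, not on 1/700.

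**Unequal sizes.** Take 18 cohorts log-spaced from 106 to 832,636.
- 1% exposed: the largest expects 832,636 × 0.01/700 = 11.9 exposed cases. The pooled OR is 1.15 if zero-cell studies are dropped, 1.39 if only studies with no cases in either group are dropped, and 1.51 if 0.5 is added to all tables with a zero cell.
- 10% exposed: the largest expects 118.9, and the pooled OR is 1.02 to 1.03.

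**A thin stratum that keeps the largest study.** Take five cohorts, one of 832,636 and four assumed between 20,000 and 200,000, with an outcome of 1/2,100 (an assumed one third of clefts). At 1% exposed the largest study expects 832,636 × 0.01/2,100 = 4.0 exposed cases; the median pooled OR is 1.44 and 15% of intervals lie wholly above 1. At 2%, 5% and 10% exposed the OR is 1.17, 1.06 and 1.03.

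**The case against.** Inverse variance suits the data described. Section 9.1 says the studies mainly report ORs and RRs, and generic inverse variance is the usual way to pool adjusted estimates; Mantel-Haenszel cannot do it. Sections 6 to 9.9 make confounding a live worry, so a crude count-based estimate is no replacement. This stands, and is why inverse variance should remain the main method. The simulations used crude tables, so they do not size the effect for adjusted ORs.

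The magnitudes rest on counts the protocol does not give, and in the sparsest settings on a zero-cell rule that it does not state. A very large study with many exposed cases would dominate a fixed-effect pool and make the shift trivial. This stands for the primary pool if exposure is common; it helps less in a stratum where even the largest study has few exposed cases.

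A separate SAP dated 10 September 2018 exists and is not shown. Zero-cell rules and sensitivity checks are commonly left there, so their absence here is not the point. The point is that the protocol selects one estimator and gives a reason that fails in sparse tables.

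A reader might infer that the pooled OR will be too high whatever the studies look like. The documents do not support that: case-control studies are included, and there the shift can be nil or reversed. A reader might also infer that the intervals are too narrow. The check shows the opposite.

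**Conclusion.** The concern holds in a conditional form. Section 9.7 states a single estimator that shifts the pooled OR upward under no effect when exposed cases are few and the comparison group is much larger. Under the assumed 18 cohorts at 20:1 the OR is about 1.4 at 1 exposed case per study, 1.1 at 5 and 1.05 at 10. The shift vanishes with groups of equal size and can fall below 1 where cases outnumber controls, which could hide a risk.

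The size in this meta-analysis cannot be stated from the protocol. With sizes spread over the reported range it runs from 1.02 to 1.03 at 10% exposed to 1.15 to 1.51 at 1%, depending on zero-cell handling. The primary pool may be little affected; the potency, route and cleft-type strata are the main exposure.

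It would overreach to speak of a formal false-positive rate for a decision. Annex 2 says that no hypothesis is tested. Section 9.7 does read intervals against 1, however, so a shift can alter the stated conclusion. Nor does the evidence support making Mantel-Haenszel the lead estimate below some fixed number of exposed cases. Any such threshold is arbitrary and would let the lead method vary between pools with the observed counts.

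**What to change.** In section 9.7:
- Extract 2x2 counts wherever published. Section 9.6 says the extraction table is still to be built, so the columns can be added.
- Keep inverse variance for the main pool and for adjusted ORs.
- For the primary pool and each subgroup, add a sensitivity estimate from the studies with counts: Mantel-Haenszel without continuity correction, or a logistic model with study as a fixed effect. Both are in metafor, the package already chosen.
- Compare it with inverse variance applied to the same crude counts, so that the contrast isolates the estimator and not the adjustment. Where the interval excludes 1 under only one of the two, report the result as dependent on the estimator.

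The cost is a few extraction columns and one extra model call per pool. The downside is that the count-based figure is crude and ignores adjustment and matching, so two estimates may need explaining.

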8.2 Secondary objective

The secondary objective of this study is:

• To perform sub group analyses for mild, moderate and strong glucocorticoid types as well as for route of administration and types of orofacial cleft.

9. **Research methods**

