9.2.1 Selection criteria used for the Systematic Literature Review (SLR)

The inclusion and exclusion criteria used for the selection of studies as well as detailed methodology of the systematic literature review are provided in the Appendix 1.

No time period restriction was used. The systematic literature review was conducted to identify all studies (including observational studies and clinical trials) published till 25 June 2018 (search date). In addition, there were no restrictions to the route of administration.

Only 18 studies were shortlisted based on the inclusion criteria. All of the 18 studies were observational studies while no clinical trials were identified that met the inclusion criteria.

The selection criteria utilized in the SLR were the following:

Inclusion criteria

- Population: Pregnant women
- Intervention: Any glucocorticoid or corticosteroid or steroids use irrespective of mode of administration
- Comparator: Any/none
- Outcomes: Incidence/ risk of cleft lip/palate in infants
- Study Design:
 - Meta-analysis and systematic literature reviews
 - Observational studies (such as cohort study, case-control study, registries data)
 - Clinical trials Phase IIb, III, and IV
 - Conference abstracts/posters
- Time period: No time period restriction
- Geography: No geography restriction

Exclusion criteria

- Population: Nonpregnant women
- Intervention: Drugs other than glucocorticoid or corticosteroid or steroid
- Outcomes: Incidence/ risk of cleft lip/palate in infants
- Study Design:
 - Animal Study

- In vitro studies
- o Editorial, letters, comment
- Clinical trials Phase I or preclinical
- Case reports, case series
- o Reviews
- Studies focusing on:
 - Diagnosis and surgical procedure for cleft repair
 - o Impact of Increased internal corticosteroids due to stress
 - The relationship between genetic mutations and cleft patients
 - Adverse events for other drugs
 - Safety profiles of glucocorticoid or corticosteroid

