9.5 Study size / Recall

18 observational studies were selected for meta-analysis by predefined eligibility criteria. For details, please refer to section 4 of systematic literature review report provided in Appendix 1.

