9.9 Limitations of the research methods

- There may have potential biases (recall and publication bias) inherent in retrospective casecontrol design. These types of study may also have higher sensitivity to detect low-frequency defects
- Included studies lacked data evaluating the relationship between dosage and duration of medication and teratogenic effects, which could affect the results of the study.
- Confounding factors assessed and described in the published sources could be an explaining factor for clinical heterogeneity, which includes the decision for a specific treatment / administration of glucocorticosteroids, but also other factors could be a reason for heterogeneityRange of dosages used is relatively wide in included studies which may have an influence on the results
- Conditions of skin, size of the skin surface treated and the part of the body where it is applied were not reported in all studies which may have an influence on the absorption of corticosteroids which may alter effect outcomes

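### Section 9.7 treats Egger's test as confirming publication bias, but it detects only funnel asymmetry, which differences between study designs can also produce

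*Protocol*

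**What the plan says.** Section 9.7 has an item headed publication bias, which opens: "Reporting or publication bias will be assessed by using the funnel plot (symmetry or asymmetry) and it again confirmed by using". The confirming tool it goes on to name is Egger's regression test, to be run only if the plot looks asymmetric. The comment under the bias section of the ENCePP checklist (Annex 2) repeats it. The same item adds a Galbraith plot to find outliers.

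Four other places bear on how a positive test would be read:

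- Section 9.2.1 lists the eligible non-trial designs: "Observational studies (such as cohort study, case-control study, registries data"). Section 9.5 says "18 observational studies were selected for meta-analysis by predefined eligibility criteria", without a breakdown by design.
- Section 9.9 warns: "There may have potential biases (recall and publication bias) inherent in retrospective casecontrol design".
- Section 9.2 gives "sample size for individual studies ranging from 106 to 832,636 patients". Standard errors are not given.
- Section 9.7 pools with a fixed effect: "We assume that the underlying effect size is the same across the studies". The subgroups in section 8.2 are potency, route and cleft type. Study design is not among them.

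**The concern.** The item sets out to answer whether studies are missing. The null hypothesis of Egger's test is different: the effect estimate has no relation to its standard error. Selective publication breaks that null, but so does anything else that makes imprecise studies differ systematically from precise ones.

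Section 9.9 names recall bias and publication bias together as possible in case-control studies, yet section 9.7 reads asymmetry as evidence of only one of them. No planned analysis separates the designs, and the checklist answers No on whether information bias is addressed.

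At stake is one conclusion in a safety review requested by a health authority. A report that publication bias was confirmed tells the reader that studies are missing. A report that the visible studies disagree by design is a different message about how far to trust the pooled odds ratio.

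**Working it through.** The protocol gives no error rate for this test, so there is no figure to reproduce. The check is whether asymmetry can arise with every study published, and how often.

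**Inputs from the protocol.** There are k = 18 studies (9.5). Cohort, case-control and registry designs were eligible (9.2.1). Recall bias is possible in case-control studies, with no size or direction given (9.9).

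**Assumptions, not in the protocol.** The test is two-sided at 5%. There are 9 cohort or registry and 9 case-control studies. Standard errors are log-uniform, 0.1 to 0.5 for cohort and 0.2 to 0.8 for case-control studies. Recall bias multiplies the case-control odds ratio by f = 1.0, 1.3, 1.5 or 2.0. The remaining between-study SD of the log odds ratio is τ = 0, 0.2 or 0.4.

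**Model.** With D = 1 for case-control and D = 0 otherwise:

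y = D·ln(f) + N(0, τ²) + N(0, SE²), no study suppressed.

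The shifts are ln(1.3) = 0.26, ln(1.5) = 0.41 and ln(2.0) = 0.69.

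**Test.** Egger's regression is y/SE = a + b·(1/SE) + error. It tests a = 0 with a t statistic on 18 − 2 = 16 df. The design-adjusted version adds c·(D/SE) and has 18 − 3 = 15 df.

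**Mechanism.** With nothing suppressed, the mean of y given SE is ln(f) × Pr(D = 1 | SE). If the designs differ in precision, that probability changes with SE, so y and SE are linked through design alone. If they have the same SE distribution, it is constant and the link vanishes.

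**Results.** Rejection rate, unadjusted / with design term, 4,000 runs per cell:

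| τ | f = 1.0 | f = 1.3 | f = 1.5 | f = 2.0 |
|---|---|---|---|---|
| 0 | 5.3% / 5.0% | 16.2% / 5.5% | 28.4% / 5.4% | 50.1% / 5.0% |
| 0.2 | 6.1% / 5.5% | 11.5% / 5.2% | 20.5% / 4.9% | 39.0% / 4.6% |
| 0.4 | 7.5% / 5.2% | 9.8% / 5.0% | 13.4% / 4.7% | 23.5% / 5.1% |

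Repeat runs of the τ = 0 and τ = 0.4 rows agreed to within about 3 percentage points.

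**Sensitivity to the assumptions.**

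- Cohorts as the less precise group, τ = 0: 16%, 27% and 51% at f = 1.3, 1.5 and 2.0.
- 6 cohort and 12 case-control studies, τ = 0: 18%, 33% and 55%.
- More separated standard errors (0.1 to 0.3 against 0.25 to 0.6), 6, 9 or 12 case-control studies, case-control less precise, τ = 0: 39 to 66% at f = 1.5.
- Equal standard errors (0.1 to 0.6 in both designs): 4 to 5% with the t version. A version with residual dispersion fixed at 1 rejects 8 to 9%, 15% and 31 to 34% at f = 1.25, 1.5 and 2.0. Section 9.7 does not name the variant.

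**Does the design term settle the cause?** No. With another factor such as route shifting the odds ratio by 1.5, balanced across designs and nothing unpublished, the design-adjusted test still rejected 23% in one illustrative setting. Conversely, with suppression confined to small case-control studies, adding the design term cut the chance of detecting it from 22% to 15% at τ = 0 and from 16% to 9% at τ = 0.4.

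**The case against.** Several points on the other side have force.

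- **The design mix is not shown.** Section 9.2.1 lists what was eligible, not what the 18 studies are. Section 9.9 makes a mix plausible but does not state the split. Sample size is no substitute for precision by design, because with a rare outcome a small case-control study can be as informative as a much larger cohort. This stands, and it is why the point is conditional.
- **Recall bias is only possible.** Section 9.9 says may, and section 9.3.1 defines exposure by redeemed prescriptions, which do not depend on recall. A reader might infer that the protocol expects recall bias in this pool. It does not go that far.
- **Heterogeneity dilutes the effect.** The protocol itself calls the evidence heterogeneous. At τ = 0.4 the rate without recall bias is already 7.5%, so recall bias adds 9.8 − 7.5 = 2.3 points at f = 1.3 and 13.4 − 7.5 = 5.9 points at f = 1.5. This also stands.
- **The wording is loose and nothing follows mechanically.** The word confirmed might refer to the asymmetry, and no exclusion or adjustment depends on the result. But the item is headed publication bias and opens with it, and no text offers another cause. The promise to discuss reasons for high heterogeneity belongs to the sensitivity analysis and is not tied to the funnel plot.
- **Covariates and test variants are analysis plan detail.** That is fair for the regression settings. What a positive test will be taken to mean is fixed in the protocol.

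Running the test only after an asymmetric plot can lower the total number of rejections, but it cannot separate the causes, since plot and test look at the same pattern.

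**Conclusion.** The point holds in a limited form. Egger's test can support a statement about funnel asymmetry. It cannot confirm publication bias, whatever the design mix. If the 18 studies include designs of different precision, the recall bias that section 9.9 allows for can produce asymmetry with nothing unpublished. Rejection is about 10 to 28% at recall factors of 1.3 to 1.5 against a nominal 5%, for an even split, the first set of assumed standard errors and τ from 0 to 0.4. With equal precision the t version is not inflated.

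Three stronger readings are not supported:

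- That the test will mislead in this particular review. The protocol text does not give the split, the standard errors or the size of any recall bias.
- That asymmetry which survives a design term may be called publication bias. Other heterogeneity, such as route, can produce it, and because section 9.9 also places publication bias in case-control studies, the design term can absorb real suppression.
- That the pooled odds ratio is wrong for this reason. Only the interpretation of the bias assessment is affected.

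**What to change.** In section 9.7, and in the matching checklist comment:

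1. Replace confirmation of publication bias with assessment of funnel asymmetry, or small-study effects.
2. Mark study design (case-control against cohort or registry) on the funnel plot.
3. Report the Egger regression without and with a design term, the second as a sensitivity analysis, and name the variant used.
4. State that neither result alone establishes or excludes publication bias, for the two reasons given in the second bullet of the verdict.

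The cost is small: one extra regression and marked points on a plot already planned. Design should be readable from the published reports. The adjusted version loses one degree of freedom and some power, and it can lose more if suppression is concentrated in case-control studies, which is why both versions should be shown.
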